17.5 Description of study population

17.5.1 Demographics and baseline characteristics

Descriptive statistics for demographics, weight, height, BMI, history of oral tobacco/nicotine use, and smoking will be presented for all subjects. All data will be listed by subject number.

17.5.2 Medical/surgical history and prior/concomitant medication

Medical/surgical history will be presented by system organ class (SOC) and preferred term (PT). Prior/concomitant medications will be presented by ATC levels 4 and 5. All data will be listed by subject number.

17.5.3 Investigational product use

The number of subjects who used each IP will be presented through listings.

17.5.4 Physical examination

Physical examination parameters will be specified as "normal", "abnormal, not clinically significant", or "abnormal, clinically significant" (as judged by the Investigator at the screening visit) and summarized.

All data will be listed by subject number.

17.5.5 Vital signs

Vital signs (systolic/diastolic blood pressure, and pulse rate) will be summarized. All data will be listed by subject number.

17.5.6 Electrocardiogram

All ECGs will be categorized as "normal", "abnormal, not clinically significant", or "abnormal, clinically significant" (as judged by the Investigator at the screening visit) and summarized.

All data will be listed by subject number.

17.6 Analysis of primary endpoint

17.6.1 Similarity in baseline-adjusted Cmax

The primary endpoint of this study is to demonstrate the similarity in baseline-adjusted C_{max} based on nicotine plasma concentrations for each of the three NP products and at least one of the two tobacco-based products.

The comparison of C_{max} between the two IPs will be assessed using a mixed model. In this model, the log-transformed C_{max} will be the dependent variable, the product will be the fixed effect, and the participant within the sequence will be the random effect. The Kenward-Roger improved method [17] will be used to estimate the denominator degrees of freedom. The estimated least square mean difference between products and the associated confidence interval (CI) will be back-transformed to the original scale to present the ratio of geometric least square means, along with the corresponding 90% CI.

Similarity between a specific NP product and a specific tobacco-based product will be assessed by reviewing the point estimates of the ratios from the model and the descriptive statistics of C_{max} per IP.

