8 STUDY DESIGN

8.1 Overall study design and schedule of events

This is a multi-center, open-label, randomized, 5-way cross-over, single-dose administration study in healthy male and female volunteers. The IPs include two flavored NP products (both 3 mg), one unflavored NP product (3 mg), and two tobacco-based snus products (4 mg and 8 mg).

The study will randomize 43 subjects to attain at least 38 evaluable subjects. An evaluable subject is defined as one with reliable C_{max} values for all five IPs.

The subjects will be healthy male and female subjects who have used oral tobacco/NP products for ≥ 1 year, with a minimum daily consumption of five pouches. Efforts will be made to include at least 17 female subjects (approximately 40%). However, a minimum of 9 female subjects (approximately 20%) will be considered acceptable.

Each subject will participate in the study for approximately 3 weeks, not including the preceding up to 4-week screening period.

An overview of the study design is shown in Figure 8.1-1. An overall schedule of events is presented in Table 8.1-1 and a detailed schedule of events for each IP use visit is presented in Table 8.1-2. Study assessments are described in Section 11.

[figure not shown]

Figure 8.1-1 Overview of the study design

The screening visit (*Visit 1*) will take place within 4 weeks prior to Visit 2 and will include an eligibility check, including evaluations of smoking and oral tobacco/nicotine use, collection of medical history, a brief physical examination, serology tests, electrocardiogram (ECG), vital signs (pulse rate and blood pressure), height, weight, and body mass index (BMI) assessments.

At Visit 2, the subjects will return to the study site for the first IP use visit.

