9.9 Randomization

At Visit 2, subjects will be randomized to one of 10 use sequences using a Latin squares William's design balancing for first-order carry-over effects. The following sequences will be randomized:

- Sequence 1: A B E C D
- Sequence 2: B C A D E
- Sequence 3: C D B E A
- Sequence 4: D E C A B
- Sequence 5: E A D B C
- Sequence 6: D C E B A
- Sequence 7: E D A C B
- Sequence 8: A E B D C
- Sequence 9: BACED
- Sequence 10: C B D A E

where

A = NP 1 - Dry, flavor A - 3 mg

- B = NP 2 Moist, flavor B 3 mg
- C = NP 3 Moist, unflavored 3 mg
- D = T1 Tobacco-based snus 1 4 mg
- E = T2 Tobacco-based snus 2 8 mg

As this is an open-label study, the IP use sequence to which each subject is allocated will be recorded in the eCRF. Computer-generated randomization lists for each site will be created using the statistical analysis software (SAS) Proc Plan, SAS Version 9.4. The randomization lists will contain the site, subject number, randomization sequence, visit, and product.

The randomization list will be generated by CTC. The original randomization list will be kept by the randomizer and copies of the randomization list will be provided to each site and to the IP packing company.

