17.2 Determination of sample size

The sample size is calculated assuming a 2x2 crossover design analyzed on log scale, using the proposed analysis model outlined under Section 17.7.1. Specifically, the expected model estimates for the equivalence between NP 1 and at least one of the two tobacco-based products are used for the power calculation (Table 17.2-1).

Input	Value	Comment
Power	>80%	Refer to the reasoning presented below this table.
Alpha	10%	Nominally set. Inference is drawn based on a 90% CI.
Hypothesized true geometric least square means ratio	0.95	
Equivalence bounds for the geometric least square means ratio	0.8 to 1.25	
Coefficient of variation	0.35	As observed in previous studies.
Assumed drop-out rate	10%	
Total sample size	43	I.e. , 43 subjects to be randomized to achieve 38 evaluable subjects for the first secondary endpoint given the assumptions above.

Table 17.2-1 Power calculation

The calculation outlined in Table 17.2-1 above renders an 80% power for one comparison of NP 1 and one of the tobacco-based products. However, as defined in the first secondary objective/endpoint, two comparisons per NP product will be made (one to each of the tobacco-based products) with the understanding that the objective is fulfilled for a specific NP product if equivalence is demonstrated to one of the tobacco-based products.

Let T1 - T2 denote the event that equivalence is found between NP 1 and tobacco products 1 and 2. The probability of demonstrating equivalence between NP 1 and at least one of the tobacco-based products can then be written as:

$1 - P(\overline{T1}) * P(\overline{T2}|\overline{T1})$

As evident by this expression, the actual power in the study will be higher than 80%. However, the conditional probabilities of the complement of T2 is unknown, due to its correlation to the preceding comparison. Therefore, the exact power cannot be determined, with the extreme scenarios being completely correlated comparisons resulting in an 80% power and completely uncorrelated comparisons resulting in an 96% power for the study.

Efforts will be made to include at least 17 female subjects (approximately 40%). However, a minimum of 9 female subjects (approximately 20%) will be considered acceptable.

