17.3.2 PK analysis set

The PK analysis set (PKAS) will consist of all subjects who used at least one IP and provided at least one evaluable PK profile, and no major deviation or AEs judged to compromise the PK analysis. Individual PK values and/or full profiles for explicit IPs may be excluded from the analysis as specified in the SAP.

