17.7 Analysis of secondary endpoints

17.7.1 Equivalence in baseline-adjusted C_{max} and AUC_{0-inf}

 C_{max} and AUC_{0-inf} for each IP will be analysed for baseline-adjusted concentrations using the same model as described in Section 17.6.1.

Equivalence for each of the three NP products and at least one of the tobacco-based products will be concluded if the 90% CI for the ratio of C_{max} and AUC_{0-inf} , respectively, from the model falls within the acceptance interval of 80.00 - 125.00%.

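### The mixed model for the primary and equivalence analyses leaves out period, a design factor of the five-period crossover

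*Protocol*

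**What the plan says.** Protocol Section 17.6.1 analyses log-transformed, baseline-adjusted Cmax with a mixed model in which "the product will be the fixed effect, and the participant within the sequence will be the random effect". Degrees of freedom follow Kenward-Roger, and results are reported as geometric mean ratios with 90% CIs. Section 17.7.1 says that Cmax and AUC0-inf "will be analysed for baseline-adjusted concentrations using the same model as described in Section 17.6.1", and concludes equivalence if the 90% CI lies within 80.00 to 125.00%. Neither section names period, and sequence appears only as the nesting label of the random participant effect.

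The design is in Section 9.9: "subjects will be randomized to one of 10 use sequences using a Latin squares William's design balancing for first-order carry-over effects", one product at each of Visits 2 to 6. The same section adds: "Computer-generated randomization lists for each site will be created". Table 17.2-1 plans for "43 subjects to be randomized to achieve 38 evaluable subjects for the first secondary endpoint given the assumptions above". The PK analysis set in Section 17.3.2 takes in "all subjects who used at least one IP and provided at least one evaluable PK profile", so subjects with incomplete periods stay in the analysis.

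**The concern.** A crossover measures each subject at successive visits, so visit order is part of the design structure. Subject and product terms cannot absorb a change that affects everyone at a given visit. If Cmax differs by visit for any reason, two things follow.

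- The change is counted as residual variation. The 90% CI on every ratio widens, and the equivalence test loses power.
- If products are not spread equally over visits, part of the change enters the product contrasts. The primary endpoint has no numerical margin and is judged from point estimates and descriptive statistics, so a shift in the estimate goes straight into that judgement.

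The model is stated outright. Sections 17.6.1 and 17.7.1 do not pass further detail to the SAP, as Sections 17.7.2 and 17.7.3 do, so this is a specification to correct and not a gap awaiting the SAP.

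**Working it through.** **Inputs from the protocol.** CV 0.35, true ratio 0.95, bounds 0.8 to 1.25, 10% dropout, 38 evaluable and 43 randomized (Table 17.2-1); decision by 90% CI (Section 17.7.1); ten sequences (Section 9.9).

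**Assumed, because the protocol does not give it.** The size of any period effect, and the allocation method (blocks or simple randomization).

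**1. The plan's own figure.** Within-subject log variance: ln(1 + 0.35²) = 0.1156. TOST power for a 2x2 crossover with SE = √(0.1156 × 2/n) and n − 2 df, at ratio 0.95 and n = 38, is 80.1% when each one-sided test is run at 10%. Dropout gives 38/0.9 = 42.2, rounded up to 43. So 38 and 43 are reproduced.

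A 90% CI, however, corresponds to 5% per side. On that rule power at n = 38 is 66.2% with 36 df. With the residual df of a joint five-product model, 38 × 5 − 1 − 37 − 4 = 148, it is 67.7%. The 67.7% is the baseline below. Its distance from 80% is a separate matter and has nothing to do with period.

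**2. Balance of the sequences.** In the ten listed sequences each product occurs twice in every period, and each of the 20 ordered pairs of neighbouring products occurs twice. The layout is sound. With complete data, period cancels from an unadjusted product contrast when every product occurs equally often in every period, which needs n divisible by 5. Here 43/5 = 8.6 and 38/5 = 7.6, so neither number allows it.

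**3. Residual inflation, present even with perfect balance.** Without a period term the residual variance becomes about 0.1156 + v, where v is the sample variance of the five period effects on the log scale (equal to 5/4 times their population variance). For a 20% drift in equal steps the effects are ln(1.00, 1.05, 1.10, 1.15, 1.20) and v = 0.00519.

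- Inflation: 0.00519/0.1156 = 4.5%.
- SE: √1.045 = 1.022, or +2.2%.

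At n = 38, 148 df, ratio 0.95 and 5% per side:

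| Assumed period effect | v | Variance | SE | 90% CI factor | Power |
|---|---|---|---|---|---|
| None | 0 | – | – | ×/÷1.138 | 67.7% |
| 10% drift | 0.00142 | +1.2% | +0.6% | ×/÷1.139 | 67.1% |
| 20% drift | 0.00519 | +4.5% | +2.2% | ×/÷1.141 | 65.4% |
| 0.2 log-unit drift (22%) | 0.00625 | +5.4% | +2.7% | ×/÷1.142 | 65.0% |
| First visit 20% higher | 0.00665 | +5.8% | +2.8% | ×/÷1.142 | 64.8% |
| 40% drift | 0.01768 | +15.3% | +7.4% | ×/÷1.149 | 60.2% |

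**4. Shift of the ratios.** Simulation with 43 allocated, 38 retained at random with complete data, 2,000 runs, six NP-versus-snus contrasts. The shift is the difference between two products in mean period effect.

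| Assumed drift | Allocation | Median shift | 95th percentile |
|---|---|---|---|
| 20% | Blocks of 10 | 0.5% | 1.5% |
| 20% | Simple | 1.1% | 3.7% |
| 40% | Blocks of 10 | 0.9% | 2.7% |
| 40% | Simple | 2.2% | 6.8% |

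The simulation does not model separate site lists or partial completers. Both can add imbalance.

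**5. Cost of the period term.** Five periods use 4 df: 148 − 4 = 144. Power with no period effect goes from 67.68% to 67.67%.

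**The case against.** The strongest reply is that the harm is small and hypothetical. No section reports or suggests a visit trend. Subjects have used snus or pouches daily for at least a year, every visit follows the same schedule after 12 h of abstinence, and Cmax is baseline-adjusted. For a 20% drift the CI factor moves only from 1.138 to 1.141. All of this stands, and the sizes above remain conditional on assumed effects.

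The planning CV is described only as coming from previous studies. If those analyses also left period out, 0.35 already contains period variation, and adding v to 0.1156 counts it twice. The protocol does not settle this, so the power losses hold only if the CV excludes period. Residual inflation also makes the equivalence test conservative; it does not raise false claims of equivalence.

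Four stronger readings may tempt a reader, and the document supports none of them:

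- *The ratios are systematically biased.* Random allocation to sequence makes the expected shift zero. What remains is chance imbalance in the realized allocation.
- *The missing fixed sequence effect is an equal fault.* Sequence is a between-subject factor, is already in the random term, and hardly affects within-subject product contrasts.
- *Balance requires multiples of ten.* Multiples of five suffice for period balance, since Sequences 1 to 5 alone form a Latin square.
- *The missing period term explains power below 80%.* That gap comes from the one-sided level used in the sample size calculation.

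Finally, Section 17 promises technical elaboration in the SAP. That lowers the urgency, but it does not excuse a model that is written out without the term.

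**Conclusion.** The point holds for period alone. Section 17.6.1, and Section 17.7.1 by reference, gives a five-period crossover a model with product as the only fixed effect. Visit differences of any size then inflate the residual, and at 43 or 38 subjects they also move the realized ratios. For effects up to about 20% the consequence is an SE 1 to 3% too large, one to three points of power, and a ratio shift usually below 1.5% with blocked allocation or below about 4% with simple randomization. These sizes rest on assumed period effects, a planning CV free of period variation, complete data from 38 subjects and one joint model for all five products. This is a modest loss of precision that can be avoided almost without cost, so it should be corrected before the data are seen.

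**What to change.** In Section 17.6.1, name product and period as fixed effects, and keep participant within sequence as the random effect with Kenward-Roger degrees of freedom. Section 17.7.1 inherits the change through its cross-reference, and the SAP should carry the same model. A fixed sequence term may be added by convention; the argument does not depend on it.

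The cost is one sentence and 4 of about 148 residual df in a five-product model, with a power change of about 0.01 percentage point. Section 17.6.1 speaks of comparing two products, which leaves open whether each pair is fitted alone. In pairwise fits, 38 complete subjects leave only 37 residual df, and the same 4 df would weigh more, so the revised sentence should say which fit is meant. The change removes additive period shifts from the ratios and returns the residual variance to its within-subject value.

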7 STUDY OBJECTIVES AND ENDPOINTS

7.1 Primary objectives and endpoints

The primary study objective and endpoint are presented in Table 7.1-1.

Table 7.1-1 Primary study objective and endpoint

Primary objective	Endpoint	Assessments	Analysis
To demonstrate the similarity in C_{max} between each of the three NP products and at least one of the two tobacco-based products.	Similarity in baseline-adjusted C _{max} based on nicotine plasma concentrations after administering single doses of the three NP products and the two tobacco-based products.	Nicotine plasma concentration analysis (Section 11.3.1)	See Section 17.6.1

C_{max}=maximum observed concentration, NP=nicotine pouch

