17 STATISTICAL METHODS AND DETERMINATION OF SAMPLE SIZE

The principal features of the statistical analysis to be performed are described in this section. A more technical and detailed elaboration of the principal features will be presented in a separate statistical analysis plan (SAP), which will be signed and approved prior to database lock.

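### The primary objective is to demonstrate similarity in Cmax, but the protocol gives no numeric criterion for similarity, so success, failure and error rate are all undefined

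*Protocol*

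**What the plan says.** The primary objective in Protocol Section 7.1, also given in the synopsis, is "To demonstrate the similarity in C_{max} between each of the three NP products and at least one of the two tobacco-based products". Section 17.6.1 repeats the verb *demonstrate* for the endpoint. It specifies a mixed model on log Cmax and back-transforms the product differences "to present the ratio of geometric least square means, along with the corresponding 90% CI". The decision then rests on one sentence: similarity between a given pouch and a given snus "will be assessed by reviewing the point estimates of the ratios from the model and the descriptive statistics of" Cmax per product. No range, hypothesis or CI condition for similarity appears in the protocol.

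Section 17.7.1 takes the same baseline-adjusted Cmax from the same model, together with AUC0-inf, and does set a criterion. Equivalence is concluded if the 90% CI "from the model falls within the acceptance interval of 80.00 - 125.00" percent. That is the first secondary endpoint, and the sample size serves it: Table 17.2-1 plans "43 subjects to be randomized to achieve 38 evaluable subjects for the first secondary endpoint given the assumptions above". Section 17.1 states that multiple comparisons are not adjusted for.

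**The concern.** A primary objective worded as a demonstration needs a rule that tells a reader, before the data, which results meet it and which do not. Section 17.6.1 supplies a review without a threshold. The only pass/fail rule and the only sample-size basis belong to a secondary endpoint on the same variable, so the two conclusions can diverge: a pouch can be reported as meeting the primary similarity objective while failing Cmax equivalence.

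The Cmax match is the purpose of the study. Sections 6.2 and 6.3.3 say that it will support abuse-liability comparisons and a possible FDA application. A similarity conclusion with no stated criterion carries little weight there.

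**Working it through.** **Inputs.** CV 0.35, 38 evaluable subjects, true ratio 0.95, bounds 0.80 to 1.25, inference from a 90% CI, 2x2 crossover on the log scale (Section 17.2 and Table 17.2-1). The synopsis uses a ratio of 1.

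**Standard error of the log ratio.**
- Within-subject SD = sqrt(ln(1 + 0.35²)) = 0.340.
- SE = 0.340 × sqrt(2/38) = 0.0780.

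**The plan's own figure.** Two one-sided tests, power integrated over the chi-square distribution of the variance estimate, df = 38 − 2 = 36:

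| Error per one-sided test | True ratio | Power at 38 | Evaluable needed for 80% |
|---|---|---|---|
| 10% | 0.95 | 80.1% | 38 |
| 5% (a 90% CI) | 0.95 | 66.2% | 52 |
| 5% (a 90% CI) | 1.00 | 75.5% | 42 |

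The stated 38 reproduces with 10% in each tail, and 38/0.90 = 42.2 rounds up to the 43 randomized. It does not reproduce with the 90% CI that the protocol uses for inference. That mismatch is a separate point. It matters here only because it sets the cost of one remedy.

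**Primary rule.** Its error rate cannot be computed, because no bound is stated. To show how much turns on the missing number, assume that similar means an observed ratio between lo and hi. For true ratio r,

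P(similar) = Φ[(ln hi − ln r)/SE] − Φ[(ln lo − ln r)/SE].

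At r = 0.80 the upper term is 1 to the accuracy shown:

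| Assumed bound | (ln lo − ln 0.80)/0.0780 | P(similar) |
|---|---|---|
| 0.90-1.11 | 1.51 | 6.5% |
| 0.80-1.25 | 0 | 50% |
| 0.75-1.33 | −0.83 | 80% |
| 0.70-1.43 | −1.71 | 96% |

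The 90% CI rule gives 5% per comparison at the same true ratio. With 0.80-1.25 on the point estimate, a true ratio of 0.75 is called similar in 20% of trials.

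**How the two conclusions can diverge.** With t(0.95, 36) = 1.688, the CI half-width factor is exp(1.688 × 0.0780) = 1.141. To pass equivalence, the estimate must lie between 0.80 × 1.141 = 0.913 and 1.25/1.141 = 1.096. An observed ratio of 0.88 has a CI of about 0.88/1.141 = 0.77 to 0.88 × 1.141 = 1.00. It fails equivalence, yet nothing in Section 17.6.1 prevents it from being called similar.

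**Across products.** These are simulations (400,000 runs) with the assumed 0.80-1.25 point-estimate bound. If all three pouches are at 0.80 of one snus and the other snus is far away, all three pass in about 25% of trials, against 0.5% under the CI rule. If a pouch is at 0.80 of one snus and 1.25 of the other, it matches at least one in 83%, against 10%.

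**The case against.** The strongest reply is that the study is partly a matching exercise. Sections 6.2 and 8.2 speak of identifying a comparable snus for each pouch, and point estimates with descriptive statistics are a reasonable way to choose a comparator. A looser primary beside a stricter secondary is not in itself a contradiction. This stands, and it makes rewording an adequate remedy. It does not rescue the verb *demonstrate*.

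A second reply is that the SAP may hold a threshold. Section 17 says that it presents principal features and that the SAP elaborates them. The SAP is not at hand, so the finding is limited to the protocol. But Sections 17.7.2 and 17.7.3 explicitly defer further detail to the SAP, and Section 17.6.1 does not. It fixes a review without a threshold as the method.

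Three stronger readings are tempting, and the documents do not support them:

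- A reader might infer that the primary objective can never fail. A review could still conclude that a pair is not similar. What is shown is that failure is undefined.
- A reader might infer that the CI is ignored. Section 17.6.1 requires it to be presented; it is simply not part of the rule.
- A reader might infer that the criterion will be settled after Cmax is known, because the study is open-label and the SAP is one "which will be signed and approved prior to database lock". Section 16.7 puts the analysis after lock, and the protocol does not say when the external laboratory releases its results. Early sight of the data is possible, not shown, and open-label use adds little for an assayed concentration.

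Finally, the protocol never applies 0.80-1.25 to a point estimate. The 50% figure follows directly from placing the cut-off at the true value, so it should be read only within the range of 6.5% to 96%.

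**Conclusion.** The point holds for the protocol as written. The primary objective is confirmatory in wording, its decision rule has no bound, and the reported 90% CI does not enter it. The primary conclusion therefore has no defined success or failure and no controlled error.

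No single figure can be put on the error. At a true ratio of 0.80 it runs from 6.5% to 96% over the bounds tried, against 5% per comparison under the existing CI rule. These figures assume 38 evaluable subjects, a CV of 0.35 and a normally distributed log ratio. The point-estimate bounds are illustrations, not protocol figures.

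**What to change.** Choose one of two changes.

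**(a) Reword.** In the synopsis, Section 7.1 and Section 17.6.1, replace *demonstrate* with *estimate* or *describe*: the Cmax ratios are reported with their 90% CIs for choosing a comparator. Reserve any claim of demonstrated comparability for the 80.00-125.00% CI rule in Section 17.7.1. The cost is wording, and the confirmatory primary claim is given up.

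**(b) Adopt the CI rule.** Make the 90% CI within 80.00-125.00% the primary Cmax criterion. The CI is already produced, but this is more than a wording change. Power at 38 evaluable must be restated as about 66% per comparison at a ratio of 0.95, or about 75% at 1.00, instead of 80%. Keeping 80% would need 52 evaluable (52/0.90, so 58 randomized) at 0.95, or 42 evaluable (47 randomized) at 1.00. The primary objective can then fail, and the stated power looks less favourable.

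In either case, fix the rule in the protocol and SAP before any plasma nicotine result is released, not merely before database lock.
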